12.15 Contact details and Out-of-hours Medical Cover

This study is moderate risk as it involves procedures above routine care. Emergency and out-of-hours medical care will be in line with usual NHS arrangements and local standard practice; no special provision is required for participants. During office hours, the CI or delegate are able to provide medical advice in relation to participation using the contact details listed at the beginning of this document.

IRAS ID: 286155 Page **58** of **73**

13 Statistical Considerations

13.1 Introduction

Details are provided on the statistical principles to be adhered to for the duration of the study including details on study design and an overview of analytical techniques.

13.2 Sample Size Estimation and Recruitment

As there are no formal hypothesis being tested, no power calculations are presented. Instead, sample size calculations are presented basis of what can reasonable recruitment estimates over the study period. The study will recruit for 36 months. With 7 sites recruiting at an expected average rate of 0.3 then a target of 70 patients is set. This is sufficient to estimate a binary endpoint with a conservative standard error of 6%.

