	Leptomeningeal disease	
	5. Informed Consent	
Exclusion Criteria:	Where the investigator considers it unsafe to undertake a lumbar	
	puncture or perform an aspiration from the Ommaya reservoir	
	Unable to comply with study procedures or give informed consent	
	3. Where the investigator considers it not in the best interest of the	
	patient to participate	
Study Centres and	Open to all UK NHS centres involved in the medical or surgical care of	
Distribution:	patients with breast cancer	
Patient Study	The patients will be followed up until death, withdrawal of consent or study	
Duration:	closure, whichever is sooner.	
Study Duration	2 years	

IRAS ID: 286155 Page **13** of **73**

Primary objectives

- To determine the feasibility of recruiting patients to undergo lumbar puncture or aspiration of Ommaya Reservoir to enable the collection of cerebrospinal fluid.
- To determine the molecular aberrations, present within CSF cell-free DNA (cfDNA).

Secondary objectives

To determine

- The proportion of cases with an actionable mutation based on CSF cfDNA findings using the TARGET (Tumour Alterations Relevant for Genomics-Driven Therapy) database.
- The concordance between CSF cfDNA and brain metastases for detected mutations (applicable where brain metastasis has been resected).
- The concordance between plasma cfDNA and brain metastases for detected mutations (applicable where brain metastasis has been resected).
- The concordance between plasma cfDNA and CSF cfDNA for detected mutations.
- The complications post-lumbar puncture or aspiration of CSF from an Ommaya reservoir (This will not apply to patients undergoing lumbar puncture at the time of neurosurgical procedure).

Exploratory objectives

 To compare the genomic landscape between paired CSF paired samples (i.e. where collected at different time points)

IRAS ID: 286155 Page **14** of **73**

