Daiichi Sankyo Europe GmBH is funding for 20 paired samples of CSF or up to 40 single CSF samples. The funding is for collection and storage at GCP Laboratories.

Make 2nds Count is funding for 7 samples of CSF. The funding is for collection, storage at GCP Laboratories and analysis at the University of Leicester.

A summary is provided below:

Funder	Number of	Diagnosis: Histologically and/or cytologically
	patients	confirmed breast cancer with CNS involvement,
		as defined as having the following:
North West Cancer	40	Metastases to the brain parenchyma
Research		
Daiichi Sankyo	20 paired samples	Metastases to the brain parenchyma or
	or up 40 single	Metastases to the leptomeninges or
	samples	
M. I. O. I. O	7	
Make 2nds Count	7	Metastases to the brain parenchyma or
		Metastases to the leptomeninges or

Chief Investigator

IRAS ID: 286155 Page **16** of **73**

[name] is the Chief Investigator for this study and is responsible for overall design and conduct of the study in collaboration with other members of the study team.

Principal Investigators/Co-Investigators

In each participating centre a principal investigator and co-investigators, part of breast and/or neuro-oncology/neurosurgical multidisciplinary teams, will be identified to be responsible for identification, recruitment, data collection and completion of CRFs, along with follow up of study patients and adherence to study protocol at site. They will also be responsible for safety reporting and processing any applicable safety information.

Clinical Trials Centre

The Liverpool Clinical Trials Centre at the University of Liverpool in collaboration with the Chief Investigator, will have overall management responsibility and will be responsible for study management activities including (but not limited to) study planning, budget administration, Trial Master File management, data management, statistical analysis and participating site coordination.

Oversight Committees

Trial Management Group (TMG)

A TMG will be formed comprising the Chief Investigator, other lead investigators (clinical and non-clinical) and members of the LCTC. The TMG are responsible for monitoring all aspects of the progress and conduct of the study and will be responsible for the day-to-day running and management of the study. The group will work with research nurses and members of the Breast Cancer Trainees Research Collaborative Group to:

- Build the clinical network to maximise recruitment opportunities

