6.1.2 Selection of Principal Investigators

Clinical co-investigators, collaborators and trainee leads will be selected at each participating site.

All principal investigators will be required to demonstrate relevant experience and commitment during early phase feasibility assessment. All investigators must have the particular medical expertise necessary to conduct the study in accordance to the protocol. Written agreement to conduct research as such will be obtained prior to site initiation.

A suitable co-investigator should be identified at each site to deputise in case of PI absence.

IRAS ID: 286155 Page **27** of **73**

7. Eligibility Criteria

The PRIMROSE CSF Study aims to recruit between 67 to 87 patients meeting the following criteria.

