13.4 Feasibility Success Criteria

The success of the study to demonstrate feasibility is primarily based on the ability of the study to recruit patients. If the observed recruitment rate is $\geq 80\%$ of this target (≥ 32 patients) it will be deemed that feasibility will have been satisfied. If between 50 - 80% (20 - 31 patients) are recruited, further studies will only be deemed feasible if actions can be taken to increase recruitment. If < 50% (19 patients or fewer) are recruited the study will have failed the feasibility criteria.

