14.9 Records Retention

The retention period for the PRIMROSE data and tissue and information is 10 years from the official End of study date.

While the current study plans to run for three years, data collection will be capped at 87 patients.

The PI at each investigational site must make arrangements to store the essential study documents (as defined by GCP guidelines) including the Investigator Site File for the full length of the study's retention period and will arrange for destruction at the end of this period as instructed by the LCTC.

The PI is also responsible for archiving all relevant source documents so that the study data can be compared against source data after completion of the study (e.g. in case of inspection from authorities). They must ensure the continued storage of the documents, even if they, for example, leave the clinic/practice or retire before the end of required storage period. Delegation of responsibility for this must be documented in writing.

IRAS ID: 286155 Page **63** of **73**

All other persons and organisations involved in the study will be responsible for storing and archiving the parts of the TMF relevant to their delegated duties.

The LCTC undertakes to archive as per their contractual requirements; documents will be archived in compliance with the principles of GCP. All eCRFs and study data will be archived onto an appropriate media for long term accessible storage. Hard copies of data will be boxed and transferred to secure premises where unique reference numbers are applied to enable confidentiality, tracking and retrieval.

IRAS ID: 286155 Page **64** of **73**

15 Regulatory and Ethical Considerations

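### The overview gives a 2-year study, but the target of 70 rests on 36 months of recruitment; at the planned rate 2 years would yield about 50 patients, so the time base must be reconciled

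*Protocol*

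**What the plan says.** The protocol gives three statements of length.

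- Section 3, overview table: "Study Duration 2 years".
- Section 13.2: "The study will recruit for 36 months".
- Section 14.9: "While the current study plans to run for three years, data collection will be capped at 87 patients".

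Section 13.2 offers no power calculation, because no hypothesis is tested. It sets the size from expected accrual: "With 7 sites recruiting at an expected average rate of 0.3 then a target of 70 patients is set". It then gives the precision at that size: "This is sufficient to estimate a binary endpoint with a conservative standard error of 6" per cent. Sections 3 and 7 give the size as a range: "The PRIMROSE CSF Study aims to recruit between 67 to 87 patients meeting the following criteria".

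**The concern.** Recruitment of 36 months cannot fit in a 2-year study. The 2 years cannot be read as follow-up per patient, because the overview has a separate row for that (until death, withdrawal or study closure). The amendment history in section 18 lists only changes to the sponsor's address and contact, so it does not explain the difference.

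The length matters here more than it usually would. The target comes from sites, rate and months, so the recruitment period is a direct input to the sample size. Recruitment feasibility is also a primary objective, with the monthly recruitment rate among its outcome measures. A site or oversight committee that works from the overview would plan for a window in which on-plan accrual does not reach the target.

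**Working it through.** **Inputs.** 7 sites, rate 0.3, 36 months, target 70, standard error 6% (section 13.2); 2 years (section 3); three years and a cap of 87 (section 14.9); range 67 to 87 (sections 3 and 7). The rate has no unit. I assume patients per site per month, the natural reading that leads to about 70.

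**Formulas.** Expected number N = sites x rate x months. Conservative standard error = sqrt(0.5 x 0.5 / N). 95% half-width = 1.96 x standard error.

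**The plan's own figures, 36 months.**
- N = 7 x 0.3 x 36 = 75.6, which is 8% above 70. The 70 follows if each site is rounded down to whole patients (0.3 x 36 = 10.8, so 10; 7 x 10 = 70), or if 0.3 is a rounded 0.278 (7 x 0.278 x 36 = 70.1). The protocol states neither convention.
- Standard error at 70 = sqrt(0.25/70) = 5.98%, which agrees with the stated 6%. Half-width 11.7 points.
- With Poisson accrual at a mean of 75.6, the chance of 70 or more is 0.76.

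**The same inputs, 24 months.**
- N = 7 x 0.3 x 24 = 50.4, which is 72% of 70.
- Standard error = sqrt(0.25/50.4) = 7.0% (7.1% at 50). Half-width at 50 is 13.9 points.
- With Poisson accrual at a mean of 50.4, the chance of 70 or more is 0.005, and of 67 or more 0.015.

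**Range for the rate.** If 0.3 is a rounded figure, it covers about 0.25 to 0.35.

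| Months | N at 0.25 | N at 0.30 | N at 0.35 |
|---|---|---|---|
| 24 | 42.0 | 50.4 | 58.8 |
| 36 | 63.0 | 75.6 | 88.2 |

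Even the top of the 24-month row lies below 67.

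**Time needed.** At 7 x 0.3 = 2.1 patients a month, 67 patients take 67/2.1 = 31.9 months and 70 take 70/2.1 = 33.3 months. Reaching 70 in 24 months would need 70/(7 x 24) = 0.42 per site per month.

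**Whether three years is enough.** If recruitment fills all 36 months and the whole study lasts three years, nothing remains after the last recruit. Section 10.4 places the patient complications questionnaire 28 ± 7 days after the procedure, so up to 35 days are needed, and section 8.2 makes this questionnaire a secondary outcome measure. Section 10.10 ends the study only when all participants' data have been analysed, which is later still.

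**The case against.** The strongest reply is that one summary row is out of date. Section 13.2 is the governing text for sample size, and section 14.9 independently supports three years. On that basis the target is within reach and the 6% is correct. This stands, and it is why the shortfall is only conditional. It does not remove the need to correct the overview.

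It can also be said that the loss is small: all analyses are descriptive, and the half-width moves only from 11.7 to 13.9 points. That is fair. The plainer effect is the missed recruitment number.

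On late recruits, the second CSF sample at 3 months is sought in 20 patients if possible and serves an exploratory objective, so late recruits need not supply it. Only the 28-day questionnaire is clearly affected, and three years in section 14.9 may be a loose reference to recruitment alone.

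Four stronger readings are tempting, but the protocol does not support them.

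- *The feasibility rule would fail at 2 years.* Section 13.4 uses fixed counts: with 32 or more patients, "it will be deemed that feasibility will have been satisfied". At a mean of 50.4 the Poisson chance of 32 or more is 0.998 if all recruits count. The footnote to the eligibility criteria limits the feasibility part to patients with brain metastases, and the protocol does not give their share.
- *The target needs all 7 sites open throughout.* Seventy patients need 70/0.3 = 233 site-months and 36 months supply 7 x 36 = 252, so about 19 are spare.
- *The 6% should rest on 47 analysed samples.* For one funder, section 4 says "The funding is for collection and storage at GCP Laboratories", and only 40 + 7 = 47 samples have analysis named in the funding text. But section 13.2 ties the 6% to a binary endpoint at the recruitment target. The schematic in section 3.1 sends samples for analysis with no split by funder, and section 11.3 stores all samples until analysis. Who pays for the rest is not stated, and that does not show the samples go unanalysed.
- *The 6% is wrong for the range 67 to 87.* It is 6.1% at 67 and 5.4% at 87, so the stated figure serves.

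**Conclusion.** The contradiction between 2 years in section 3 and 36 months or three years in sections 13.2 and 14.9 is real, and it concerns an input to the sample size. A reader might infer that the target of 70 and its precision cannot be delivered. That follows only if the 2-year row governs, and two of the three statements point the other way. If it did govern, about 50 patients would be expected (42 to 59 over the plausible rounding of the rate), with a standard error of about 7%, short of both 70 and 67. This rests on reading 0.3 as per site per month and on using all 24 months for recruitment; follow-up inside the 2 years would lower the number. If 36 months governs, the target and the 6% stand, and what remains is a wrong overview row and a three-year total with no room for the last questionnaires. This is a consistency correction.

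**What to change.** State one recruitment period and a separate, longer total study duration, in the same terms in sections 3, 13.2 and 14.9. The total should cover at least the 28 ± 7 day questionnaire for the last recruit and should agree with the end-of-study definition in section 10.10. Give the unit of the 0.3 rate in section 13.2.

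- If recruitment is 36 months, correct the overview row; the target and the 6% can stay.
- If recruitment is 24 months, restate the expected number as about 50 and the standard error as about 7%, and revise the 67 to 87 range to match.

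The cost is protocol wording. No analysis changes, and the stated precision worsens only in the 24-month case.

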13.3 Outcome Measures

Aside from recruitment, feasibility measures will also be taken on the rate of patients recruited to those eligible, the ability of patients and clinicians to adhere to study protocol (measure via the number of major/minor deviations) and the ability of the study to collect data (measured as the number of complete CRFs returned and metrics on the QC and data query issues).

13.4 Feasibility Success Criteria

The success of the study to demonstrate feasibility is primarily based on the ability of the study to recruit patients. If the observed recruitment rate is $\geq 80\%$ of this target (≥ 32 patients) it will be deemed that feasibility will have been satisfied. If between 50 - 80% (20 - 31 patients) are recruited, further studies will only be deemed feasible if actions can be taken to increase recruitment. If < 50% (19 patients or fewer) are recruited the study will have failed the feasibility criteria.

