5.3 Risks and Benefits

5.3.1 Potential Risks

This study involves collecting CSF via lumbar puncture (with atraumatic needle) or from aspiration of CSF from in situ Ommaya reservoirs form patients with CNS involvement secondary to breast cancer. For the majority of patients this will be an extra procedure, although in a small number of cases it will be performed as part of routine care. Potential risks and side effects of the procedures include infection (rare), nerve root irritation (in a minority of patients), headaches and back pain.

To minimise risk lumbar punctures will be performed using appropriate local anaesthesia by clinicians experienced in the procedure. Furthermore, atraumatic needles will be used which are associated with significantly less side effects than conventional needles for lumbar punctures. Where patients are undergoing a neurosurgical procedure, the lumbar puncture will be carried out once patient has been anaesthetised so reducing any side effects. Patients will be followed up to understand the side effects if any that occur post procedure.

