5.4 Aims and Objectives

5.4.1 Primary objectives

- To determine the feasibility of recruiting patients to undergo lumbar puncture or aspiration of Ommaya Reservoir to enable the collection of cerebrospinal fluid.
- To determine the molecular aberrations, present within CSF cell-free DNA (cfDNA).

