7.4 Co-enrolment Guidelines

Participants can be recruited into other trials during their participation in this study. This will be documented as part of the follow up process. Individuals who have participated in any other studies or trials of any medicinal product can also be enrolled onto this study if eligible.

IRAS ID: 286155 Page 28 of 73

^{*}These patients will be recruited for the feasibility part of the study.

8. Outcomes

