8.1 Primary Outcomes

Objective	Outcome Measure
To describe the feasibility of recruiting	Quantitative measurement of study feasibility will be
patients to undergo lumbar puncture	measures as the ability of the study to recruit patients
to enable collection of cerebrospinal	and obtain clinical data for analysis. Specifically:
fluid.	RECRUITMENT
	Recruitment rate: defined as the total number of patients randomised per month
	Site opening: defined as the time take to open
	the target number of sites
	STUDY PROTOCOL
	 Patient adherence to protocol: to determine whether patient and /or care givers adhere to the conditions of the protocol, measured via the number of minor or major protocol deviations Review of the practicality of delivering interventions SAMPLE SIZE INFORMATION The estimation of quantities required for an accurate sample size calculation, such as standard deviation of the outcome measure DATA COLLECTION
	The proportion of expected CRFs returned and the rate of missing key data items
	,
	PATIENT ACCEPTABILITY
	Estimate drop-out rates
	Participation rates

IRAS ID: 286155 Page **29** of **73**

To determine the molecular	This will be measured by quantifying the proportion of
aberrations, present within CSF cell-	genomic aberrations in all collected types of cfDNA
free DNA (cfDNA).	samples. The outcome will be percentage of specific of
	aberrations observed in samples as a proportion of all
	aberrations observed.

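### The feasibility cut-offs in 13.4 are sized for the 40-patient brain-metastasis cohort, but neither 13.4 nor 8.1 says that only those patients count

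*Protocol*

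**What the plan says.** Protocol 13.4 makes recruitment the main test of feasibility: "The success of the study to demonstrate feasibility is primarily based on the ability of the study to recruit patients". At 80% or more of its target (32 patients or more), "it will be deemed that feasibility will have been satisfied". The middle band is introduced by "If between 50 - 80% (20 - 31 patients) are recruited", and in that band further studies depend on action to raise recruitment. The failure band ends with "19 patients or fewer) are recruited the study will have failed the feasibility criteria". No diagnosis is named in any band. The target is referred to but not restated, and the only target given earlier in section 13 is the 70 in 13.2.

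Section 7.1 admits three diagnostic groups: newly diagnosed BCBM, progressive BCBM and leptomeningeal disease. The first two carry an asterisk and the third does not. The footnote, printed after 7.4, says: "These patients will be recruited for the feasibility part of the study". The overview in section 3 places the asterisks the same way.

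Section 4 says that the lead funder pays for the feasibility study, with 40 samples, and its row in the funder table covers parenchymal brain metastases only. The rows for the other two funders also admit leptomeningeal metastases. They cover 20 paired or up to 40 single samples, and 7 samples.

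Section 8.1 defines the recruitment rate from the total number of patients per month, with no restriction by diagnosis. On procedure, its objective reads "patients to undergo lumbar puncture" and does not mention the reservoir, whereas 5.4.1 reads "To determine the feasibility of recruiting patients to undergo lumbar puncture or aspiration of Ommaya Reservoir to enable the collection of cerebrospinal fluid".

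**The concern.** The protocol defines a feasibility cohort by diagnosis and then states a go/no-go rule that does not refer to it. The cut-offs fit that cohort, but the count does not have to come from it. If everyone recruited is counted, a threshold meant for 40 BCBM places is applied to a study of 67 to 87 places.

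The rule decides whether further studies are deemed feasible. If the counted population is settled only after recruitment is known, the same data could support a satisfied, middle-band or failed result. Correcting the target to 40 would not cure this, because the population counted would still be unnamed.

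**Working it through.** **1. Reproduce the cut-offs.** The inputs are 80% and 50% (13.4), 40 (section 4) and 70 (13.2).

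- Against 40: 0.80 × 40 = 32 and 0.50 × 40 = 20, so failure is 19 or fewer. All three figures in 13.4 are reproduced exactly.
- Against 70: 0.80 × 70 = 56 and 0.50 × 70 = 35. Neither is reproduced. As shares of 70, the printed cut-offs are 32/70 = 45.7% and 20/70 = 28.6%.

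The cut-offs were therefore built on the 40-patient parenchymal cohort.

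**2. Places open to leptomeningeal disease.** The inputs are the funder table in section 4 and the sample size range in section 7.

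- Lower end: 40 + 20 + 7 = 67, so 67 − 40 = 27 places may be leptomeningeal.
- Upper end: 40 + 40 + 7 = 87, so 87 − 40 = 47 places may be leptomeningeal.

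**3. Permitted extremes.** The fewest BCBM patients needed to reach a total of 32 is max(0, 32 − places open to leptomeningeal disease).

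- 27 places: 32 − 27 = 5 BCBM patients, and 5/40 = 12.5%, far below the 50% failure line.
- 47 places: 47 exceeds 32, so 0 BCBM patients are needed.

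**4. Less extreme mixes.** The share of recruits with leptomeningeal disease only is not given in the protocol, so 10% to 50% is an assumed range. With 32 recruits in all, the expected BCBM count is 32 × (1 − share).

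| Assumed share | BCBM count | Percentage of 40 |
|---|---|---|
| 10% | 28.8 | 72% |
| 20% | 25.6 | 64% |
| 30% | 22.4 | 56% |
| 40% | 19.2 | 48% |
| 50% | 16.0 | 40% |

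Every row is below 80%, and the last two are below 50%. In whole patients at a total of 32, one leptomeningeal-only recruit leaves 31 BCBM patients (middle band), and 13 leave 19 (failure band). The all-patient count reads as satisfied in both cases.

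**5. When the two counts agree.** If every place is filled and the 40 parenchymal places are used as funded, 40 BCBM patients are recruited and both counts pass. At a total of 70, the all-patient count misleads about the upper cut-off only if more than 70 − 32 = 38 recruits are leptomeningeal-only. The discrepancy therefore matters when BCBM recruitment falls short, which is the situation the rule exists to detect.

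**The case against.** The strongest reply is that 13.4 does not say every patient counts; it is silent. The match to 40, the footnote and the lead funder's row together suggest that the BCBM cohort was intended. A statistical analysis plan, not at hand here, might spell that out. The analyses are exploratory, 13.4 says recruitment is the primary and not the only basis, and 13.3 lists other feasibility measures. The extremes are also unlikely: the other two funders' places admit parenchymal disease too, and a patient with both parenchymal and leptomeningeal disease meets an asterisked criterion.

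Much of this stands. The extremes are limits and not forecasts, and the intention can reasonably be inferred. But the protocol itself fixes the decision rule and its numbers, and the nearest target and the outcome definition in 8.1 both point to an all-patient count. That is a conflict within the protocol, not detail left for later.

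A reader might also infer that patients sampled from an Ommaya reservoir, under anaesthetic at neurosurgery, or in routine care should not count. The documents do not support this:

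- The objective in 5.4.1 includes the reservoir, and the footnote restricts by diagnosis, not by procedure.
- Sampling at neurosurgery is a planned route (9.2 and 9.5). Section 5.4.2 excludes lumbar puncture at neurosurgery from the complications objective, and no such exclusion is made for feasibility.
- On routine care, 5.3.1 says only "although in a small number of cases it will be performed as part of routine care" and draws no consequence for the count.

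What remains on procedure is the difference in wording between 8.1 and 5.4.1.

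**Conclusion.** The point holds for diagnosis. Section 13.4 applies cut-offs derived from 40 BCBM patients to a count whose population is not named, next to a target of 70 that covers all diagnoses. As written, the rule can return a satisfied result while BCBM recruitment is in the middle or failure band. At a total of 32, one leptomeningeal-only patient is enough for the first case and 13 for the second; the outer limits are 5 and 0 BCBM patients.

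These figures assume that the funder table governs how places are used and that the patients concerned have leptomeningeal disease without an asterisked criterion. The documents do not allow an estimate of how likely any given mix is, and they do not show that the sponsor intends to count all patients. The procedure wording in 8.1 is a smaller, separate inconsistency and does not bias the verdict.

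**What to change.** State in 13.4 and 8.1 that only patients meeting an asterisked BCBM criterion count toward the feasibility cut-offs, and name 40 as the target. The cut-offs then stay as printed. Report leptomeningeal-only recruitment separately.

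If the sponsor means all patients to count, amend the section 7 footnote and rescale the cut-offs to the all-patient target. With 70 these would be 56 or more, 35 to 55, and 34 or fewer.

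Either way, reconcile the procedure named in 8.1 with the one in 5.4.1.

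The cost is a wording amendment, with no added procedure for patients. Eligibility is already confirmed on a study form (9.3), but the form should show which of the three diagnostic criteria was met, because the protocol does not list that as a separate item. The downside of the first option is that fewer patients count, so the verdict may be less favourable. The choice should be made before the recruitment total is assessed.

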3.1. Schematic the Study

Prior to enrolment

Patient Identification: Patients with CNS involvement secondary to breast cancer identified via breast and neuro-oncology/neuro-surgical departments, multi-disciplinary teams and clinics at involved UK centres.

- Obtain patient consent

Inclusion Criteria

- Informed Consent
- Male or female
- ≥16 years of age
- Any ER, PgR or HER2 status
- Newly diagnosed with BCBM*
- Progressive BCBM following either local or systemic treatment*
 - o or
- · Leptomeningeal disease

Exclusion Criteria

- Where the investigator considers it unsafe to undertake a lumbar puncture or perform an aspiration from the Ommaya reservoir
- Unable to comply with study procedures or give informed consent
- Where the investigator considers it not in the best interest of the patient to participate

At registration

- Patient enrolled on study

When scheduled

- Data collection and Routine/Diagnostic Tissue Collection

As soon as possible after procedure

 a) CSF extraction Procedure (along with blood sample collection pre-lumbar puncture/Ommaya Reservoir aspiration)

At routine visit or over the phone

- Post-procedure complications assessment for clinician (as soon as is feasible on a paper or eCRF)
- b) Post-procedure complications assessment **for patient** (28 days ± 7 days post-procedure at routine clinical visit or via phone

Paired Sample Collection (n = 20 if possible): Patients will be consented for a paired sample collection where they will be required to attend a second visit for lumbar puncture or Ommaya Reservoir CSF collection after 3 months of first CSF extraction or at disease progression (cranial or non-cranial). Follow procedures a), b) and c).

All samples sent to the GCP Lab for storage until sample collection end.

Samples sent to Cancer Research Lab in Leicester for analysis

Follow up end, Study Outcome Measures

IRAS ID: 286155 Page **15** of **73**

4. Roles and Responsibilities

Sponsor

The Sponsor is the University of Liverpool and is legally responsible for the study. They will formally delegate specific sponsoring roles to the Chief Investigator and Clinical Trials Centre.

Funders

North West Cancer Research is the lead funder for this study. It is funding the feasibility study the collection of 40 CSF samples of CSF, storage at GCP Laboratories and analysis at the University of Leicester.

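### The feasibility cut-offs in section 13.4 are 80% and 50% of 40, but the only target stated in section 13 is 70, so the denominator and the population counted must be named

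*Protocol*

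**What the plan says.** Section 13.2 of the protocol gives the recruitment assumptions, "With 7 sites recruiting at an expected average rate of 0.3", and the period, "The study will recruit for 36 months"; it continues "then a target of 70 patients is set". It attaches a precision statement to that number: "This is sufficient to estimate a binary endpoint with a conservative standard error of 6" per cent.

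Section 13.4 makes recruitment the main test of feasibility. It refers back to a target without giving its value, and pairs each percentage with a count: 80% or more with at least 32 patients (feasible), 50 to 80% with 20 to 31 patients (further studies feasible only if recruitment can be improved), and below 50% with the outcome "19 patients or fewer) are recruited the study will have failed the feasibility criteria".

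The number 40 does not appear in section 13. It appears in section 4 under Funders, where the lead funder's contribution is described: "It is funding the feasibility study the collection of 40 CSF samples of CSF". The funder table gives that funder 40 patients with metastases to the brain parenchyma. In section 7.1 the two brain-metastasis criteria carry an asterisk and leptomeningeal disease does not; the asterisk note reads "These patients will be recruited for the feasibility part of the study".

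Section 8.1 gives the recruitment measure as "Recruitment rate: defined as the total number of patients randomised per month".

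**The concern.** Feasibility of recruitment is the first primary objective. No hypothesis is tested, and section 13.4 contains the protocol's pass, conditional and fail limits for that objective. The rule states each limit twice, once as a percentage and once as a count, and the two do not agree on the one target that section 13 provides. A reader applying the percentages and a reader applying the counts could reach different conclusions from the same recruitment total. If the ambiguity is left until recruitment is known, the denominator would be chosen with the result in view.

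The population is open in the same way. If the limits belong to a 40-patient brain-metastasis part, section 13.4 does not say so, and its unrestricted word for those counted would let leptomeningeal patients contribute.

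**Working it through.** **Inputs.** Target 70, 7 sites, rate 0.3, 36 months and standard error 6% (section 13.2); cut-offs 32, 20 to 31, and 19 (section 13.4); overall range 67 to 87 (section 7); funder numbers 40, 20 paired or up to 40 single, and 7 (section 4).

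**1. Is 70 the working target of section 13?** With a proportion of 0.5, SE = √(0.25/n). At n = 70 this is √(0.25/70) = 5.98%, which reproduces the stated 6%. At n = 40 it is √(0.25/40) = 7.9%. So 70 is used in the section and is not a stray figure.

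**2. Which denominator gives the printed counts?** Cut-offs are 0.8 × target and 0.5 × target, rounded up to whole patients.

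| Candidate target | 80% | 50% | Fits 32 and 20? |
|---|---|---|---|
| 70 (section 13.2) | 56 | 35 | no |
| 67 (lower end of range) | 53.6, so 54 | 33.5, so 34 | no |
| 87 (upper end of range) | 69.6, so 70 | 43.5, so 44 | no |
| 7 × 0.3 × 36 = 75.6, so 76 (assuming 0.3 is per site per month; no unit is given) | 60.8, so 61 | 38 | no |
| 40 (lead funder, section 4) | 32 | 20 | yes |

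Of these, only 40 works, and it also gives failure at 19 or fewer (19/40 = 47.5%).

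**3. Where do counts and percentages disagree if the target is 70?**

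| Total recruited | Share of 70 | By count | By percentage |
|---|---|---|---|
| 19 or fewer | up to 27.1% | failed | failed |
| 20 to 31 | 28.6 to 44.3% | conditional | failed |
| 32 to 34 | 45.7 to 48.6% | feasible | failed |
| 35 to 55 | 50.0 to 78.6% | feasible | conditional |
| 56 or more | 80% or more | feasible | feasible |

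The disagreement covers 12 + 3 + 21 = 36 consecutive totals, from 20 to 55. The full success-against-failure clash is confined to 32, 33 and 34.

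**4. Is 40 a coherent sub-target?** The funder numbers add up to the overall range: 40 + 20 + 7 = 67 and 40 + 40 + 7 = 87. So 40 is a recognisable component of the study. The other two funders' rows also admit leptomeningeal disease, so the whole-study count and the feasibility-part count are not the same quantity.

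**The case against.** The strongest reply is that the counts are correct and only the label is missing. Section 4 ties the lead funder's 40 samples to the feasibility study, the funder table restricts that row to brain parenchyma, and the section 7 footnote assigns the asterisked brain-metastasis patients to the feasibility part. The three places are consistent with one another, and 40 reproduces every printed cut-off. On that reading 32 is 80% and no total is misclassified.

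This stands as an account of what was probably meant. It limits the point: a reader might infer that the plan passes a study that has missed half its target, and the documents do not support that as a fact. It follows only if 70 is the denominator, and then only for totals of 32 to 34. Nor should one infer that recruitment is counted without any time limit: section 13.2 gives 36 months, although section 13.4 does not repeat it.

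The reply does not remove the defect. The reference in section 13.4 can only lead back, within section 13, to 70. It does not mention 40, does not point to section 4 or to the section 7 footnote, and does not limit the patients counted. Nor is this detail left for an analysis plan: the protocol fixes these cut-offs itself.

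**Conclusion.** The mismatch is certain: section 13.4 pairs its percentages with counts that belong to 40, while the only target in its section is 70. Which side is wrong cannot be settled from the protocol. If 70 is intended, the success and failure limits are too low by 24 patients (56 − 32) and 15 patients (35 − 20), and totals from 20 to 55 receive two different verdicts. If 40 is intended, the limits are right but the denominator and the eligible population are unstated, so leptomeningeal patients could be counted towards a brain-metastasis question. These results are direct arithmetic on printed figures; they need no assumption about accrual or the unit of the 0.3 rate. Because the rule decides the first primary objective, it should be corrected before the feasibility result is read.

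The word randomised in the section 8.1 rate definition is a separate, minor slip. The study has a single arm and section 9.4 describes registration only. It does not affect the cut-offs.

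**What to change.** Choose one of two corrections, and do so before feasibility is judged.

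- **(a) Keep 70.** Restate section 13.4 as feasible at 56 or more, conditional at 35 to 55, failed at 34 or fewer, counted over the 36-month recruitment period of section 13.2.
- **(b) Use the feasibility part.** Name 40 in section 13.4 as the feasibility target, keep 32, 20 to 31, and 19, count only newly diagnosed or progressive brain-metastasis patients with a cross-reference to the section 7 footnote, and state the period over which they are counted. The protocol gives no accrual rate for this subgroup, so the period has to be set by the sponsor and cannot be derived from the whole-study rate.

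In section 8.1, replace randomised with registered.

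The cost is protocol wording only; no procedure or data item changes. Under (a) the success threshold becomes less favourable, rising from 32 to 56. Under (b) the threshold stays at 32 but fewer patients count towards it.
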